#### Exclusion from Participating in the Active Treatment:

12) Reduction in the mean number of drinks consumed per week by 50% or more between the phone screen and the in-person screening or report of average drinks per day falling within safe levels of alcohol consumption (i.e. 2 drinks/day for males and 1 drink/day for females by the HHS standard) two weeks prior to screening.

## **SECTION J: RECRUITMENT**

**Provide a summary of the recruitment process, including who will recruit, when and where recruitment will occur, and how subjects will be identified**

**Note: Submit any recruitment materials such as advertisements, brochures, flyers, letters/e-mails, scripts, etc. Please submit these materials as separate documents in either Word or PDF format.**

A recruitment team of 3-4 approved study staff will be responsible for recruiting participants for this study. The recruitment team will use the IRB approved flyers to advertise across multiple recruitment sources. Participants will be recruited via web, radio, newspaper, digital billboard, movie theaters, and Massachusetts Bay Transportation Authority (MBTA) advertisements:

**Web Ads:**

Online advertisements will be placed on several recruitment platforms (e.g., Facebook, Craigslist).

**Radio Ads:**

Advertisements will be submitted to local radio stations.

**Newspaper Ads:**

Advertisements will be put in local area newspapers.

**MBTA Ads:**

Advertisements will be placed on MBTA trains, buses, and stations.

**Digital Billboard Ads:**

Digital advertisements (e.g., the study flyer) will be used for recruitment.

**Movie Theater Ads:**

Advertisements will be played on screens in movie theaters.

The recruitment team will also liaise with colleagues in local area hospitals to make the study known to fellow professionals in the Boston area.

A telephone screening will be conducted to determine the initial eligibility of people who are interested in participating in the study. Potential participants who pass the telephone screening will be identified by their name and phone number, which will be kept in a password-protected database as outlined in Sections M, P, and Q of this application. Following the telephone screening, potential participants will be invited to the Center for Anxiety and Related Disorders at Boston University for an in-clinic screening session to further assess their eligibility for this study. Only those who pass this in-clinic screening will be included in the study and assigned participant numbers, which will be kept separate from any identifiable information.

Timeline:

Recruitment will begin approximately 3 months after obtaining IRB approval, during Year 1 of the study. Approximately 3-4 new participants will be recruited per month. We anticipate recruiting 5 participants in Year 1, 25 participants in Years 2 and 3, 30 participants in year 4, and 15 participants in Year 5.

## **SECTION K: CONSENT AND ASSENT**

NOTE: Please refer to the consent and assent form templates on the IRB website when creating your consent/assent documents. The templates include the required elements of consent and will help to ensure that your consent/assent form meets the requirements of the federal regulations and the BU CRC IRB. The consent templates can be located at:

<http://www.bu.edu/orc/forms/human-subjects/>.

**Provide a summary of the consent process, including who will consent, and when and where consent will occur. The summary should include, as appropriate, any waiting period between informing the prospective participant and obtaining consent, that the prospective participant or the legally authorized representative has sufficient opportunity to consider whether to participate, and steps taken to minimize coercion or undue influence.**

**Note: Submit copies of all consent forms and scripts. Please submit these materials as separate documents in Word format.**

Potential participants who meet eligibility criteria for this study following the telephone screening will be invited to the Center for Anxiety and Related Disorders at Boston University for an in-clinic screening to further assess their eligibility for the study. At the screening, participants will be provided an informed consent form to read over. However, the information in the informed consent should not be entirely foreign to them, as they will be given general information about the study at the initial telephone screening. All areas of the consent form will be verbally reviewed with the patient prior to obtaining written consent:

- 1) The purpose and duration of the study
- 2) Assessment and treatment procedures
- 3) Risks and benefits
- 4) Issues related to confidentiality

Participants will be informed that participation in the study is voluntary and that they have the right to withdraw from the study at any time without penalty.

Before a participant signs the informed consent, study staff will:

- 1) Answer any questions/concerns raised by the participant; and
- 2) Measure the participant's blood alcohol concentration (BAC) using a breathalyzer, to ensure that the participant provides written informed consent while sober (BAC=0.00%).

- If the participant's BAC is greater than 0.00% before signing the informed consent, he/she would have to reschedule the screening, which can be a few hours later or another day. If asked to reschedule, the participant will be asked not to drive home and

to make other transportation arrangements. If no one is available to take the participant home, a study staff member may call a taxi or car service. CARD will cover transportation expenses in this circumstance.

After the participant signs the consent form, they will receive a copy of it. Prior to conducting the first neuroimaging procedure at BU CILSE, study staff will also review the imaging procedures with the participant.

The consent form also specifies that data from the present study (#4299) will be combined with data from the supplemental study (#4890E) if participants sign consent for both studies.

For all other study sessions, participants with BAC levels greater than 0.02% will be asked to remain at the center until their levels reach below 0.02, or reschedule if necessary. Again, if a participant is drunk and is asked to reschedule the appointment, the participant will be asked not to drive home and to make other transportation arrangements. If no one is available to take the participant home, a study staff member may call a taxi or car service.

The first study session will be scheduled within 4-weeks after their in-clinic screening. If the one-month window expires before the participant can come in to CARD again, then the in-clinic screening session will have to be repeated to assess the participant's eligibility for the study.

Participants who meet eligibility for the study following the telephone and in-clinic screening will be notified of their eligibility to participate in our study via telephone by our study staff. Potential participants will be told that they can take up to two weeks to notify us of whether they would like to participate in this study or whether they need more time to decide. Potential participants who need more time to decide, will be told that they can contact us again whenever they're ready, as long as the study hasn't ended. However, as noted above, if there has been more than one-month between the screening and the participant's first treatment session, we may have to repeat the screening process to ensure eligibility for enrollment at that point in time.

**Indicate the consent and/or assent process and document(s) to be used in this study. Check all that apply**

Consent: Adults (≥21 years of age)		N/A 
One of the following MUST apply		
	Consent Form/Information Sheet	
	Verbal Consent (Script) Note: If written consent will not be obtained, complete the 'Waiver of Written Documentation Consent' box (Box 1) located further down in this section	
	Consent will not be obtained Note: If consent will not be obtained, complete the 'Waiver or Alteration of Consent' box (Box 2) located further down in this section	

Assent of Children (<18 years of age)	N/A 
--	---

One of the following MUST apply	
	Assent Form OR Parent Consent Form/Information Sheet (older children may sign the parent consent form along with their parents as long as the consent form is written at the grade level of the subjects)
	Verbal Assent (Script)
	Assent will not be obtained  If assent will not be obtained, one of the following conditions must exist:  1.  The capability of some or all of the children is so limited that they cannot reasonably be consulted  2.  The children are too young to provide assent  3.  The intervention or procedure involved in the research holds out the prospect of direct benefit to the health or well-being of the children and is available only in the context of the research  4.  The research meets the same conditions as those for waiver or alteration of informed consent in research involving adults, as specified in the regulations at 45 CFR 46.116(d)*. (Complete the 'Waiver or Alteration of Consent' box (Box 2) located further down in this section)

*45 CFR 46.116(d):  http://www.hhs.gov/ohrp/humansubjects/guidance/45cfr46.html
	

Guidance on age requirements for obtaining assent:
 
 
● Parental Permission for minors under 6 years of age
 
● Verbal assent for minors 6-11 years of age
 
● Written assent from minors ages 12-17 (unless verbal consent is approved for the parents/adult subjects)
 
	
Parental Permission	N/A 
One of the following MUST apply	
	Parental Consent Form
	Parental Verbal Consent (Script)

Note: If written consent will not be obtained, complete the 'Waiver of Written Documentation of Consent' box (Box 1) located further down in this section
	
	Parental permission will not be obtained  If parental permission will not be obtained, one of the following conditions must exist:

	
1.  The research protocol is designed to study conditions in children or a subject population for which parental or guardian permission is not a reasonable requirement to protect the subjects (for example, neglected or abused children).
 
2.  The research meets the same conditions as those for waiver or alteration of informed consent in research involving adults, as specified in the regulations at 45 CFR 46.116(d)*. (Complete the 'Waiver or Alteration of Consent' box (Box 2) located further down in this section)
 
*45 CFR 46.116(d):  http://www.hhs.gov/ohrp/humansubjects/guidance/45cfr46.html

--	---

Consent: Cognitively Impaired Adults (<math>\geq 18</math> years of age)      N/A 
 
Describe the process for the consent and/or assent process for enrolling cognitively impaired adult subjects including how capacity to consent is determined and if there is continual assessment of capacity
	
N/A	

Assent will be obtained from:
 
 All Subjects   Some Subjects, specify:   No Subjects
	
	Consent will be obtained from the subject's Legally Authorized Representative (REQUIRED)


CONSENT OF NON-ENGLISH SPEAKING SUBJECTS      N/A 
 
Describe the process for obtaining consent from non-English speaking subjects. List the individual who will serve as the interpreter and his/her qualifications.
 
NOTE: A copy of the translated consent along with the Attestation Form for Translation of Consent must be submitted. The Attestation Form can be located at:  http://www.bu.edu/irb/application-forms/
	
N/A	

**BOX 1—WAIVER OF WRITTEN DOCUMENTATION OF CONSENT**

WAIVER OF WRITTEN DOCUMENTATION OF CONSENT N/A 
 
Either Criteria 1 or 2 must be met in order to qualify
		Yes	No

 Criteria 1
			

The research is NOT FDA Regulated
			

The only record linking the subject and the research would be the consent document		
The principal risk would be potential harm resulting from a breach of confidentiality		
Each subject will be asked whether the subject wants documentation linking the subject to the research and the subject's wishes will govern		
A written statement/information sheet will be provided to subjects. If NO , provide rationale for not providing this information		
□ Criteria 2		
The research is NOT FDA Regulated		
The research presents no more than minimal risk of harm to subjects		
The research involves no procedures for which written consent is normally required outside of the research context		
A written statement/information sheet will be provided to subjects. If NO , provide rationale for not providing this information		

## **BOX 2—WAIVE OR ALTERATION OF CONSENT**

WAIVER OR ALTERATION OF CONSENT	N/A 	Yes	No
All of the criteria below must be met in order to qualify			
The research is NOT FDA Regulated			
The research involves no more than minimal risk to the subjects			
The waiver or alteration will not adversely affect the rights and welfare of the subjects			
The research could not practicably be carried out without the waiver or alteration			
Whenever appropriate, the subjects will be provided with additional pertinent information after participation. If NO , provide rationale for not providing this information:			
Provide the justification/rationale for why this study meets the above criteria for waiving or altering consent (REQUIRED):			

## **SECTION L: STUDY PROCEDURES**

**In the box below provide a detailed description of the study procedures to be performed (preferably in sequential order). Be sure to specify which procedures are for research purposes versus which procedures are part of standard of care, if applicable. Be sure to include the following information:**

- **Methods of data collection**
- **Details regarding research activities/procedures/interventions**
- **Number, frequency, duration and types of subject contacts (visits, phone calls, internet surveys, mailings, etc.)**
- **Time required from each subject**

- **Use of equipment (eye-tracker, treadmill, sensors, etc.). Provide a brief description of equipment that will be used in the study.\***

**\*Note: The IRB may request more information about the equipment (including equipment manuals) and/or request that you submit Appendix C: Device Form.**

**Submit copies of all surveys, interview questions, assessments, screening scripts, etc. that will be used during the conduct of this study. Please submit these materials as separate documents in either Word or PDF format.**

**Note: If subjects will have standard of care procedures in addition to research procedures, clearly state which procedures are standard of care and which are for research purposes only**

#### Overview

Potential participants will complete a telephone and an in-clinic screening to determine eligibility for this study. Eligible participants will be randomized to receive one of two treatment conditions: 1) Zonisamide plus *Take Control* (a computerized alcohol reduction and medication compliance program developed by the National Institute on Alcohol Abuse and Alcoholism (NIAAA)); 2) a placebo plus *Take Control*. For both conditions, participants will receive 12 treatment sessions. Participants will receive medication at each session, and they should have two weeks worth of medication on hand at any given time. Participants will take the medication as prescribed at home. The first 11 treatment sessions will include *Take Control*. The 12 treatment sessions will be followed by two drug dose taper sessions, and a follow up phone interview immediately following the final session.

Participants will also undergo two scans of less than 2 hours duration, one before they begin study sessions and the second near the end of the study (12th study week and before the medication taper). At the in-clinic screening session, participants will receive a “MRI Information for Research Participants” handout that answers some commonly asked questions about MRI and tells participants what they can expect while undergoing an MRI scan. Both scans will be conducted at BU CILSE. Participants will be screened before each scan session for pregnancy (urine sample, women of childbearing potential only), recent smoking or alcohol use (breathalyzers), and illicit substance use (urine sample). Participants will be asked to complete the Alcohol Urge Questionnaire (AUQ) before and after the scan. Participants will also be asked to complete item #8 from the AUQ before and after the Alcohol Cues Task. Eligible participants will complete a 1-hour 3 Tesla MRI scan involving structural imaging (MRI) and functional imaging (fMRI). The fMRI scans include a resting-state scan (no task involved) a cognitive (Stroop) task, and an alcohol cue reactivity task. The latter two scans involve presentation of visual images to participants while they are in the scanner. No contrast agent or invasive procedures are used. Only personnel trained in working in high magnetic field environments will work on this project. Imaging data will be analyzed on secure networks using only encrypted files. All data obtained will be coded to protect participant privacy and confidentiality.

One month following completion of study treatment (study week 16), participants will be asked to complete a follow-up telephone assessment.

The entire study is estimated to be completed in five years. The first six months to nine months of the project will be dedicated to hiring, training and certifying staff. Recruitment will begin within three months of obtaining IRB approval, during Year 1 of the study. Approximately 3-4 new participants will be recruited per month. We anticipate recruiting a total of 5 participants in Year 1, 25 participants in Years 2 and 3, 30 participants in year 4, and 15 participants in Year 5. The last third of Year 5 will be devoted to completion of data entry and data management procedures, preliminary analyses, and the preparation of manuscripts.

### Screening Procedures

#### I. Telephone Screening

Individuals interested in participating in our study will be evaluated for initial eligibility by a telephone screening lasting 15-20 minutes in duration. This will be conducted by trained study staff that will follow the attached telephone screening script. The Alcohol Use Disorders Identification Test (AUDIT) will be used to help determine eligibility. If initial study eligibility is met, potential participants will be contacted via telephone to schedule a date for an in-clinic screening session. General information about the study will also be provided during this telephone screening.

#### II. In-clinic Screening

If a participant is eligible to complete the in-clinic screening session following the telephone screening, the in-clinic screening session will be conducted to ensure his/her eligibility for enrollment in the study. This 4-hour session will be conducted at the Center for Anxiety and Related Disorders at Boston University. Screening may be completed in a single visit or over multiple visits (e.g. a hematology or chemistry test needs to be repeated). If the participant completed a screening session for study #4617 within a 1-month window of their scheduled screening session for this study, the results from the duplicate assessments can be transferred to this study without being repeated.

The following procedures will be conducted during the in-clinic screening:

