### Randomization

Participants who continue to be eligible for the study following the in-clinic screening will be randomized to one of two treatment conditions: 1) Zonisimaide and *Take Control* (TC) computerized program; 2) a placebo and TC. An adaptive randomization will be used, where gender, heavy drinking, handedness, and smoking status will be variable levels.

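### Screening results carried over from study #4617 can be about eight weeks old at the first session, and a carried-over drinking calendar may miss the two weeks that exclusion 12 asks about

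*Combined protocol and SAP*

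**What the plan says.** The carry-over rule is in Section L, II. In-clinic Screening. Its condition is "If the participant completed a screening session for study #4617 within a 1-month window of their scheduled screening session for this study"; its consequence is that "the results from the duplicate assessments can be transferred to this study without being repeated". The rule exempts no assessment and does not say which assessments the two studies share.

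The age limit on screening data is in Section K. "The first study session will be scheduled within 4-weeks after their in-clinic screening". Beyond that, "If the one-month window expires before the participant can come in to CARD again, then the in-clinic screening session will have to be repeated". Further down, the same section puts the limit more softly: "if there has been more than one-month between the screening and the participant's first treatment session, we may have to repeat the screening process".

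Exclusion 12 (Section I, under exclusion from active treatment) has two limbs. One is a fall of at least 50% in mean weekly drinks between the phone screen and the in-person screening. The other is average daily drinking already within the safe level "two weeks prior to screening".

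Eligibility is settled at screening. Under Randomization in Section L, "Participants who continue to be eligible for the study following the in-clinic screening will be randomized to one of two treatment conditions". Table 1 has a week-1 column, and its note places those assessments before treatment starts.

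**The concern.** Section K treats screening data as good for about a month. The carry-over rule lets data that may already be a month old enter at the point where Section K's clock starts. A participant who comes through #4617 can therefore be randomized on results older than the plan accepts for anyone screened directly.

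Two things are at stake. Some entry criteria describe a current state, and an old result may not show it. Exclusion 12 in particular keeps out people who have already cut down before treatment. Drinks per day is the measure behind the main power calculation, and drinking is the subject of aim 4 in Data Analysis, so the plan has a direct interest in applying that criterion to data from the right days.

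**Working it through.** **Inputs**
- Carry-over window: 1 month (Section L, In-clinic Screening). The length in days is not given; I assume 28 to 31. I read the window as running before this trial's screening, since the #4617 session must already be complete.
- Screening to first session: 4 weeks = 28 days (Section K).
- The plan's limit on screening age: 4 weeks or one month, so 28 to 31 days (Section K).
- Exclusion 12 look-back: 14 days before screening (Section I).
- TLFB duration: about 10 minutes for 90 days of data (Section L, III. Alcohol Use Related Assessments).

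**Step 1. Age at first session**

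Maximum age = carry-over window + screening-to-session window.

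| Route | Calculation | Days | Relative to the plan's limit |
|---|---|---|---|
| Screened directly | 28 | 28 | within the limit |
| Carried over, 28-day month | 28 + 28 | 56 | 56/28 = 2.0 |
| Carried over, 30-day month | 30 + 28 | 58 | 58/30 = 1.9; 58/28 = 2.1 |
| Carried over, 31-day month | 31 + 28 | 59 | 59/31 = 1.9; 59/28 = 2.1 |
| Both windows a full 31-day month | 31 + 31 | 62 | 62/31 = 2.0 |

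The central reading gives 56–59 days, about twice the limit. This is a worst case: both windows must be fully used.

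**Step 2. What exclusion 12 can see**

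For a TLFB taken *d* days before this trial's screening, the days observed in the 14-day window are max(0, 14 − *d*).
- *d* = 7: 14 − 7 = 7 of 14 days.
- *d* = 10: 14 − 10 = 4 of 14 days.
- *d* above 14: 0 of 14 days.

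The carry-over rule permits *d* up to 28–31, so a permitted TLFB can show nothing of the window. For the 50% limb, a TLFB from #4617 may also predate this trial's phone screen, in which case the two measurements are in the wrong order. The documents do not give the interval between phone screen and in-clinic screening, so how often that would happen cannot be worked out.

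**Step 3. What inclusion 4 can see**

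Inclusion 4 needs a 28-consecutive-day period within the 90 days before screening. Assuming a 90-day look-back, a TLFB 30 days old covers 90 − 30 = 60 of those days. That is enough to show a qualifying 28-day period.

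**Step 4. What is refreshed before treatment**

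| Item | Week-1 entry in Table 1 |
|---|---|
| TLFB, blood tests, pregnancy test, urine drug screen, concomitant medications, MINI Suicidality | yes |
| ADIS-5 diagnostic interview | no |
| Medical history | no |
| Physical exam (listed for in-clinic screening) | no row in the table |

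Section L, IV. Biological Assessments puts the first on-study assessments on the day medication starts. Neither that section nor Table 1 says results must be available, or compared with the entry criteria, before the first dose.

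**The case against.** The strongest reply is that fresh data are collected anyway. Table 1 repeats drinking, laboratory, pregnancy, drug-screen, medication and suicidality assessments before treatment. The Overview in Section L adds pregnancy, alcohol and drug checks before the first scan, and the Covid-19 Protocols require a laboratory visit for blood and urine at screening. A reader might infer from the carry-over rule that current drinking, laboratory values or suicide risk go unassessed before treatment. The documents do not support that. What remains is narrower: randomization follows screening eligibility, and no text turns the week-1 results into an eligibility check.

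The second reply is that the rule is permissive and limited to duplicate assessments. The content of #4617's screening is not described, so it is not established that any particular item, the TLFB included, is shared. This stands, and it limits what can be said about reach. It does not remove the conflict, because the rule exempts nothing.

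The third concerns exclusion 12. A reader might conclude that the criterion cannot be applied to transferred participants at all. That goes too far. Nothing waives the criterion, the telephone screen is a separate step, and the TLFB is a retrospective calendar, so the missing days can be recovered. The supported statement is that exclusion 12 cannot be evaluated from a TLFB more than 14 days old taken alone.

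Finally, a reader might suspect that two routes of entry bias the treatment comparison. Transfer happens before randomization, so it does not of itself favour an arm, and the drinking models adjust for baseline. The documents show no such bias.

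**Conclusion.** The concern holds as a gap between rules. A carried-over result can be about 56–59 days old at the first session, roughly twice the plan's own limit, because the limit is counted from this trial's screening and not from the date of the result. For ADIS-5, medical history and physical exam, no week-1 repeat is scheduled. For the other items listed above, week-1 data exist but have no stated role in eligibility. The sharpest conflict is with exclusion 12, where a permitted TLFB may contain none of the required 14 days.

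This rests on a month of 28–31 days, full use of both windows, and the item in question being among the duplicates. The number of participants entering through #4617 is not given and could be zero, so no effect on power or on the estimate can be calculated. Separately, Section K contradicts itself: it first makes repetition mandatory and then says "we may have to repeat the screening process to ensure eligibility for enrollment at that point in time".

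**What to change.** Three edits to the protocol:

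1. In Section L, In-clinic Screening, state that when results are carried over from #4617, the Section K limit runs from the date of the earliest transferred eligibility assessment. The maximum age at the first session then returns to 28–31 days, a ratio of 1.0.
2. In the same place, require any transferred TLFB to be updated to the date of this trial's screening before exclusion 12 is applied. A full bar on transferring the TLFB for inclusion 4 is not needed, as step 3 shows.
3. In Section K, reconcile the two statements on repeating the screening so that one rule applies throughout.

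The cost falls on #4617 transfers only: about 10 minutes for the TLFB, going by the protocol's own figure for 90 days of data, and occasional repetition of other screening items when the limit has run out.
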